8.4 Reporting Adverse Events

All SAEs (related and unrelated) will be recorded from the signing of the consent form until 28 days following the end of treatment. Any SAEs considered possibly or probably related to the treatment and discovered by the Investigator at any time after the study should be reported. All SAEs must be reported to Lumen Bioscience within one business day of the first awareness of the event. The Investigator must complete, sign and date the SAE pages, verify the accuracy of the information recorded on the SAE pages with the corresponding source documents, and send a scanned copy by email to Lumen Bioscience

Additional follow-up information, if required or available, should all be scanned and emailed within one business day of receipt, and this should be completed on a follow-up SAE form placed with the original SAE information, and kept with the appropriate section of the CRF and/or study file.

Lumen Bioscience is responsible for notifying the relevant regulatory authorities of certain events. It is the PI's responsibility to notify the HREC of all SAEs that occur at his or her site. Investigators will also be notified of all unexpected, serious, drug-related events (7/15 Day Safety Reports) that occur during the clinical trial. Each site is responsible for notifying its HREC of these additional SAEs. Lumen is responsible for AE reporting to the FDA and/or other relevant national regulatory authorities.

9 INVESTIGATIONAL RECORD KEEPING

All study records including disposition of the drug (i.e., dates, quantity, use by subjects, and unused supplies) and subject CRFs, source documents, consent forms, and chart notes will be maintained and retained in accordance with local regulatory requirements and U.S. federal regulations set forth by 21 CFR Sec. 312.62. Each subject case history will contain documentation confirming that informed consent was obtained for the subject prior to participation in the study. All personnel associated with this study will make their best effort to ensure anonymity and confidentiality of subject records. Individual electronic CRFs will be collected for each subject. A copy of each CRF will be retained at the clinical site in the Investigator's files until further notice from Lumen Bioscience. All original CRFs will be transferred to Lumen Bioscience or its appointed agent for analysis and storage.

Case histories and study records will be made promptly available upon request to Lumen Bioscience, its representative, Australian Therapeutic Goods Administration (TGA) personnel, or Food and Drug Administration personnel. Lumen Bioscience, with the PI, will furnish required periodic study progress reports to the HREC. Any SAE safety reports will be made available immediately to Lumen Bioscience, the HREC, and the TGA in accordance with regulatory requirements. The study results will be disseminated through presentations at scientific meetings and submission for publication to a peer-reviewed medical journal and clinicaltrials.gov. All subject identifiers will be removed in order to maintain subject confidentiality. At the conclusion and publication of the study results, a summary of the results will be shared with study participants in a letter from the PI.

Anticipated secondary uses of the data include supporting regulatory applications to other regulatory agencies for investigational or marketing approval and patent applications. In addition, the data from this study will be used in regulatory filings for other indications, for example, safety and PK data.

9.1 **Protocol Deviations and Amendments**

Any deviation from protocol deemed appropriate to prevent potential harm to an individual subject does not require pre-approval from the clinical site HREC or authorities at Lumen Bioscience or its representative; however, such deviations must be promptly reported to the HREC and Lumen Bioscience or its representative. Please consult the Study Manual for additional instructions.

9.2 Study Monitoring

Before an investigational site can enter a subject into the study, a representative of Lumen Bioscience, Inc. will visit the investigational study site to:

- Determine the adequacy of the facilities.
- Discuss with the Investigator(s) and other personnel their responsibilities with regard to protocol adherence, and the responsibilities of Lumen Bioscience or its representatives. This will be documented in a Clinical Study Agreement between Lumen Bioscience and the Investigator.

During the study and at the close-out of the study, a monitor from Lumen Bioscience or its representative will have regular contacts with the investigational site, for the following:

- Provide information and support to the Investigator(s).
- Confirm that facilities remain acceptable.
- Confirm that the investigational team is adhering to the protocol, data is being accurately recorded in the CRFs, and investigational product accountability checks are being performed.
- Perform source data verification. This includes a comparison of the data in the CRFs with the subject's medical records at the hospital or practice, and other records relevant to the study. This will require direct access to all original records for each subject (e.g., clinic charts).

- Record and report any protocol deviations not previously sent to Lumen Bioscience, Inc.
- Confirm AEs and SAEs have been properly documented on CRFs and confirm any SAEs have been forwarded to Lumen Bioscience or its representative and those SAEs that met criteria for reporting have been forwarded to the HREC and/or TGA.

The monitor will be available between visits if the Investigator(s) or other staff needs information or advice. The PI assumes ultimate responsibility for the conduct of the study and remains readily accessible throughout the duration of the study.

9.3 Audits and Inspections

Authorized representatives of Lumen Bioscience, a regulatory authority, or HREC may visit the site to perform audits or inspections, including source data verification. The purpose of a Lumen Bioscience audit or inspection is to systematically and independently examine all study-related activities and documents to determine whether these activities were conducted, and data were recorded, analyzed, and accurately reported according to the protocol, GCP guidelines of the ICH, and any applicable regulatory requirements. The Investigator should contact Lumen Bioscience immediately if contacted by a regulatory agency about an inspection.

The Investigator agrees to allow the monitor to inspect the drug storage area, study drug stocks, drug accountability records, subject charts and study source documents, and other records relative to study conduct.

To ensure compliance with GCP and all applicable regulatory requirements, Lumen Bioscience may conduct one or more quality assurance audits.

9.4 Retention of Records

The Investigator must maintain all documentation relating to the study for a period of at least 2 years after the last marketing application approval, or, if not approved, 2 years following the discontinuance of the test article for investigation. If it becomes necessary for Lumen Bioscience or the Regulatory Authority to review any documentation relating to the study, the Investigator must permit access to such records.

10 HUMAN RESEARCH ETHICS COMMITTEE (HREC)

The final clinical protocol, the final version of the Patient Informed Consent Form, and recruitment materials must be approved, or given a favorable opinion, in writing by an HREC as appropriate. The PI must verify that the HREC has approved the clinical protocol, Patient Informed Consent Form, and recruitment materials for the investigation prior to conducting study evaluations. Initial HREC approval, and all materials approved by the HREC for this study

including the Patient Informed Consent Form and recruitment materials must be maintained by the Investigator and made available for inspection.

The PI is responsible for informing the HREC of any amendment to the protocol in accordance with local requirements. The protocol must be re-approved by the HREC upon receipt of amendments and biannually, as local regulations require.

The PI is also responsible for providing the HREC with reports of any reportable serious adverse drug reactions from any other study conducted with the investigational product. Lumen Bioscience will provide this information to the PI.

Progress reports and notifications of serious adverse drug reactions will be provided to the HREC according to local regulations and guidelines.

10.1 Ethical Conduct of the Study

The study will be performed in accordance with ethical principles that have their origin in the Declaration of Helsinki and are consistent with ICH/GCP, the National Statement on Ethical Conduct in Human Research, and applicable regulatory requirements.

10.2 Written Informed Consent

The PI or research staff designee will ensure that the subject or legally authorized representative is given full and adequate oral and written information about the nature, purpose, possible risks and potential benefits of the study. The subject or legally authorized representative must also be notified that the subject is free to discontinue from the study at any time. The subject or legally authorized representative should be given the opportunity to ask questions and allowed time to consider the information provided.

The subject's signed and dated informed consent, or the signed and dated informed consent of a legally authorized representative, must be obtained before conducting any study procedures. The PI must maintain the original, signed Patient Informed Consent Form. A copy of the signed Patient Informed Consent Form must be given to the subject or legally authorized representative.

12 APPENDICES

12.1 Appendix A. Common Terminology Criteria for AEs

## **1. INTRODUCTION**

The following Statistical Analysis Plan (SAP) provides the outline for the statistical analysis of the data from the CAM01 study.

The planned analyses identified in this SAP may be included in clinical study reports (CSRs), regulatory submissions, or future manuscripts. Also, post hoc exploratory analyses not necessarily identified in this SAP may be performed to further examine study data. Any post hoc, or unplanned, exploratory analyses performed will be clearly identified as such in the final CSR.

## **2. PROJECT OVERVIEW**

### **2.1 Study Design**

The study will consist of two-parts: Part A, an open-label administration of a single dose of LMN-101 and Part B, a randomized, double-blind, placebo-controlled, dose-escalation study of 3 dose levels of LMN-101.

In Part B, healthy volunteers will take LMN-101 or placebo orally at one of three dose levels three times daily over 28 days. Study observation will continue until 4 weeks after the last dose of study drug. Healthy volunteers will be recruited from the community by media and from the existing clinical research center population of healthy volunteers. Individuals meeting all inclusion and exclusion criteria will be sequentially assigned to Part A and then Part B. In Part A, participants will be assigned to a single dose of 3000 mg PO given as six 500-mg capsules of LMN-101 (2 participants).

In Part B, participants will be sequentially assigned to escalating dose regimens and will be randomized within each dose regimen to active or placebo treatment:

- 300 mg PO three times daily (TID) given as a single 300-mg capsule of LMN-101 orally for 28 days (4 participants) or identical-appearing placebo capsule (2 participants).
- 1000 mg PO TID given as two 500-mg capsules of LMN-101 orally three times daily for 28 days (4 participants) or identical-appearing placebo capsules (2 participants).
- 3000 mg PO TID given as six 500-mg capsules of LMN-101 orally three times daily for 28 days (4 participants) or identical-appearing placebo capsules (2 participants).

For both study parts, protocol-specified evaluations and procedures will be performed on days 1-2 and at one- to two-week intervals during dosing. Study observation will continue until 4 weeks after the last dose of study drug. For Part A, the follow up visit occurs on Day 29, while for Part B the follow up visit occurs on Day 56.

Enrolment is planned for 20 participants: Part A, 2 participants, and Part B 18 participants (LMN-101: 12 participants; placebo: 6 participants), 6 per dose cohort (LMN-101: 4 participants per dose cohort; placebo: 2 participants per dose cohort).

Study Days are defined as consecutive calendar days beginning from the start time of the first study drug administration for each participant (Day 1). Protocol-specified evaluations and procedures will be performed on Days 1, 2, 8, 15, 28 (Part B only), and 29, with an additional evaluation 4 weeks after the final dose at Day 56 for Part B. There will be an interim safety review between each dose cohort. Study observations will continue until 4 weeks ( $\pm$  1 week) after the last dose of study drug.

### **2.2 Objectives**

#### **2.2.1 Primary Objective**

The primary objective of this study is to determine the safety and tolerability of LMN-101.

#### **2.2.2 Secondary Objectives**

The secondary objectives of this study are to determine:

- Serum pharmacokinetics (PK) of LMN-101; and
- Formation of anti-drug antibodies.

### **2.3 Endpoints**

#### **2.3.1 Primary Endpoint**

The primary endpoint will be safety and tolerability of LMN-101.

### **2.3.2 Secondary Endpoints**

The secondary endpoints for this study are:

- Peak serum VHH concentration following administration of the initial dose and peak serum VHH concentration following a course of treatment (if systemic absorption is observed).
- Area under the serum VHH concentration versus time curve (AUC) following administration of the initial dose and following a course of treatment (if systemic absorption is observed).
- Induction of serum anti-VHH IgG antibodies (if systemic absorption is observed).

### **2.4 Sample Size**

A maximum of 20 healthy volunteers will be enrolled in this study, consisting of 2 in Part A and 18 in Part B: cohorts 1 to 3. If a participant was enrolled and discontinued before starting study drug, they will be replaced in the study. A participant who withdraws after dosing but before completing the full study will be replaced if they have not completed at least three weeks of study drug (apart from Part B, Cohort 3 where there will be no replacements).

The sample size is not based on formal power calculations as this study is designed only to provide an initial assessment of the safety and PK of LMN-101 in healthy participants.

### **2.5 Randomization**

This will be a two-part study: Part A, an open-label administration of a single dose of LMN-101 and Part B, a randomized, double-blind, placebo-controlled, dose-escalation study of 3 dose levels of LMN-101.

Two participants in Part A will be allocated to a single dose of 3000 mg PO (orally) treatment of LMN-101. Participants in Part B will be allocated to treatment, according to the master randomization schedule produced by Novotech (Australia) Pty Ltd, manually by the study site.

As Part B participants are enrolled into the study, participants will be assigned to a unique randomization number.

If a participant was enrolled and discontinued before starting study drug, they will be replaced in the study. A participant who withdraws after dosing but before completing the full study will be replaced if they have not completed at least three weeks of study drug. There will be a single set of replacement participants.

Randomization numbers are randomly assigned to treatment according to the specified randomization scheme. In each of Part B cohorts 1 to 3, four randomization numbers will be randomly assigned to LMN-101 and 2 will be randomly assigned to placebo. A maximum of 2 healthy volunteers will be enrolled in Part A and 18 healthy volunteers in Part B: Cohorts 1 to 3.

### 3. STATISTICAL CONSIDERATIONS

This study is a dose-escalation study with the goal of assessing the safety and tolerability of LMN-101. The general analytical approach for all endpoints will be descriptive in nature. No formal statistical hypothesis testing will be conducted. No p-value will be presented due to the small sample size of this study. Data will be handled and processed according to the sponsor's representative (Novotech (Australia) Pty Ltd) Standard Operating Procedures (SOPs), which are written based on the principles of GCP (Good Clinical Practice.)

#### 3.1 General Considerations

All data collected on the eCRFs will be presented in the data listings and will be listed and sorted by study part, cohort, treatment, subject ID number and visit (timepoint), where applicable. All summaries will present the data by study part and treatment group, as applicable.

Unless otherwise stated, the following statistical approaches will be taken:

- **Continuous variables:** Descriptive statistics will include the number of non-missing values (N), mean, standard deviation (SD), median, minimum, maximum.

The appropriate precision for derived variables will be determined based on the precision of the data on which the derivations are based, and statistics will be presented in accordance with the abovementioned rules.

When reporting descriptive statistics, the following rules will apply in general:

- o n will be an integer.
  - o Arithmetic mean, SD and median will use 1 decimal place more than the original data to a maximum of 3 decimal places.
  - o Minimum and maximum will be reported using the same number of decimal places as the original value.
  - o Geometric mean, geometric SD, and geometric CV% will be employed for PK parameter summaries.
- **Categorical variables:** Descriptive statistics will include frequency counts and percentages per category. Percentages will be rounded to one decimal place, with the denominator being the number of participants in the relevant population with non-missing data, unless otherwise specified.

Percentages displayed based on continuous data (e.g., percentage changes from Baseline) will be displayed to 1 decimal place. Unless otherwise stated, the denominator for the percentages will be based on the number of study participants in the respective analysis set and treatment arm.

- **Baseline:** Baseline values will be defined as the last valid, non-missing observation for each participant prior to dosing of study drug on Day 1.
- **Follow-up:** For Part A, the follow up visit occurs on Day 29, while for Part B the follow up visit occurs on Day 56. Follow-up data is defined as the last valid, non-missing observation for each participant after the final day 1 dosing event for Part A and final day 28 dosing event for Part B. For Part B participants follow up data will be collected on day 56 and will be required for comparison to in study data for hematology, chemistry and coagulation results. For participants where no follow up data is available, there will be no comparison between follow up data and in study data.
- **Repeat/Unscheduled assessments (Safety):** No repeat/unscheduled assessments will be included in summary presentations (Tables, Figures). All repeat/unscheduled

assessments captured in the Electronic Data Capture (EDC) system will be presented in the data listings.

- **Assessment windows:** All assessments will be included in the data listings and no visit windows will be applied to exclude assessments that were performed outside of the protocol specified procedure windows.
- **Date and time display conventions:** The following display conventions will be applied in all outputs where dates and/or times are displayed:
  - Date only: YYYY-MM-DD
  - Date and time: YYYY-MM-DD/HH:MM

If only partial information is available, unknown components of the date or time will be presented as 'NK' (not known), i.e., '2016-NK-NK'. Times will be reported in military time.

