### 3.2 Key Definitions

- **Baseline:** The baseline value is defined as the last available valid (quantifiable continuous or categorical value), non-missing observation for each participant prior to first study drug administration. Repeat and unscheduled assessments will be included in the derivation of the baseline values.
- **Change from Baseline:** The change from baseline value is defined as the difference between the result collected/derived at a post-baseline visit/time point and the baseline value.

The change from baseline value at each post-baseline visit/time point will be calculated for all continuous parameters using the following formula:

$$\text{Change from Baseline Value} = \text{Result at Visit/Time Point} - \text{Baseline Value}$$

The change from baseline value will only be calculated if the specific post-baseline visit/time point result and the baseline value for the parameter are both available and will be treated as missing otherwise.

- **Percent Change from Baseline**

Percent Change from Baseline at each post-baseline visit/time point will be calculated for all continuous parameters using following formula

$$\% \text{ Change from Baseline} = 100 \times \frac{(\text{Post-Dose Visit Value} - \text{Baseline})}{\text{Baseline}}$$

- **Study day:** The study day of an event is defined as the relative day of the event starting with the date of the first study drug administration (reference date) as Day 1 (there will be no Day 0).

Relative days for an event or measurement occurring before the date of first dose will be calculated as follows:

$$\text{Relative Day} = \text{Event Date} - \text{Date of First Dose}$$

The relative day for an event or measurement occurring on or after the reference date to the date of the last dose will be calculated as follows:

$$\text{Relative Day} = \text{Event Date} - \text{Date of First Dose} + 1$$

There is no relative Day 0. Relative day will not be calculated for partial dates in cases where relative day is shown in a data listing.

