#### **12.3.1 Endpoints**

Hematology:

- Hemoglobin
- Leukocytes
- Neutrophils
- Eosinophils
- Monocytes
- Lymphocytes
- Basophils
- Platelets
- Other

Serum Chemistry:

- Sodium
- Potassium
- Calcium
- Magnesium
- Phosphate
- Creatinine
- Albumin
- AST
- ALT
- Alkaline phosphatase
- Total bilirubin
- eGFR
- Other

Coagulation:

- aPTT
- INR

All laboratory data collected at scheduled and unscheduled visits will be included in the listings, but only results collected as scheduled visits will be included in the summary tables excepts for baseline assessment where unscheduled visit prior to first study medication could be considered for baseline summary.

Results for individual parameters may be reported in different units depending on the analysing laboratory. If required, the results (and the corresponding normal range cut-off values) for

individual parameters may be converted to International System of Units (S.I.) units to summarize the data.

For all the parameters where a unit value has been reported, the parameter names that will be used in the outputs will comprise of the test name and the unit of measure, for example, 'Albumin (g/L)'. For the urinalysis parameters, the parameter name will be the reported test name only. Parameters will be sorted alphabetically within tables and listings.

For all parameters where a normal range limit value was reported, the normal range will be derived based on the available lower and upper limit values and any reported mathematical symbols. If both a lower and upper limit value is available, the normal range will be presented as '(Lower, Upper)'.

The reported results for each parameter with a defined normal range will be classified ('Low', 'Normal', 'High') in relation to the defined normal range limits. If a result is equal to the normal range cut-off value, the result will be considered 'Normal'.

The decimal precision to which the summaries for each parameter will be based on the maximum number of decimals to which the reported result or the normal range limits are presented to in the raw data. The results and normal ranges will be displayed to the same decimal precision in the listings.

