If a result for a parameter that is normally considered continuous is reported as a range (i.e., the result for basophils is reported as '<0.01' for a single time point), the result may be converted to a numeric as noted in section 3.5 to contribute to the derivations and the summary statistics. Any conversion rules that are applied will be highlighted in the footnotes of the affected tables and listings. The original reported result value will however be included in the listing.

The haematology, coagulation and serum chemistry results tables will present summary statistics for each laboratory parameter within the specific test panel. For each parameter, summaries will be presented for the baseline and each scheduled post-baseline visit. In addition, summaries will be presented for the change from baseline values at each scheduled post-baseline visit.

Additionally, counts (%) of number participants with values out of normal range at each scheduled time point will also be presented along with shift tables that will represent the changes in normal range categories across post-baseline time points. Clinical significance for out of range values will be listed only.

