### **12.4.1 Definition of variables**

- Heart Rate (beats/min),
- Systolic blood pressure (SBP) (mmHg),
- Diastolic blood pressure (DBP) (mmHg),
- Respiratory rate (breaths/min),
- Temperature (°C).

All vital signs data collected at scheduled and unscheduled visits will be included in the listings, but only results collected as scheduled visits will be included in the summary tables.

The parameter names that will be used in the outputs will comprise of the test name and the unit of measure, for example, 'Systolic Blood Pressure (mmHg)'. Parameters will be sorted in

the order that the measurements were collected in on the Vital Signs eCRF page within the tables and listings.

The change from baseline to the pre-dose assessment at each post-baseline visit will be calculated for all parameters. An assessment of clinical significance for each result will be reported.

The decimal precision to which the summaries for each parameter will presented will be based on the maximum number of decimals to which the results were reported on the eCRF.

Vital signs measurements will present summary statistics for the results at the baseline and each scheduled post-baseline visit for each of the parameters. In addition, summaries will be presented for the change from baseline values and interpretation of each result at each scheduled post-baseline visit.

The listings of vital signs measurements will include all the information collected. In addition, the observations that are used as the baseline record (value) for each parameter will be flagged, and the change from baseline values at each post-baseline visit will be presented.

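### A non-serious laboratory, blood pressure or pulse abnormality seen only at an unscheduled visit can be missing from every safety table and appear only in listings

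*SAP*

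**What the plan says.** The general rule for safety data in SAP 3.1 is "No repeat/unscheduled assessments will be included in summary presentations (Tables, Figures". The same item sends these results to listings: all such "assessments captured in the Electronic Data Capture (EDC) system will be presented in the data listings".

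The detailed sections agree with it:

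- **Laboratory, SAP 12.3.1:** "only results collected as scheduled visits will be included in the summary tables excepts for baseline assessment". The exception lets an unscheduled visit before the first dose be considered for baseline. Out-of-range results are tabulated as "counts (%) of number participants with values out of normal range at each scheduled time point", and the shift tables run by post-baseline time point. The clinical significance of an out-of-range value is listed, not tabulated.
- **Vital signs, SAP 12.4.1:** "only results collected as scheduled visits will be included in the summary tables".
- **Mock tables, general comments:** unscheduled visits are left out of summary tables.
- **Baseline, SAP 3.2:** "Repeat and unscheduled assessments will be included in the derivation of the baseline values".

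Protocol 8.3 governs whether an abnormal value becomes an adverse event. It says that clinically significant changes in laboratory results, blood pressure and pulse do not have to be reported as AEs, because the data listings will hold them. The exceptions are values that amount to an SAE or cause treatment to be stopped.

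**The concern.** Safety and tolerability is the primary endpoint. Protocol 3.3 names clinically significant laboratory abnormalities and changes in vital signs among the measures of safety. SAP 3 and 3.3 make the analysis purely descriptive, so the tables are the formal summary of the result.

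Under the rule, an abnormal value obtained between planned visits after dosing cannot enter a by-visit summary, a shift table or an out-of-range count. The AE tables would be the natural second route, but Protocol 8.3 largely closes it for laboratory values, blood pressure and pulse. A table could then show no abnormality at a dose level where one was observed and judged clinically significant.

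**Working it through.** There is no power or sample-size figure behind this point, so there is nothing of the plan's own to reproduce. The check follows one value through the plan and then works out what one participant weighs.

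**Step 1: when can an abnormality fall between scheduled draws?** The Schedules of Evaluations (Protocol Tables 3 and 4) place post-dose laboratory draws as follows:

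- Part B: Days 8, 15, 28 and 56. Gaps counted from Day 1: 8 − 1 = 7, 15 − 8 = 7, 28 − 15 = 13, 56 − 28 = 28 days.
- Part A: Days 8, 15 and 29. Gaps: 7, 7, and 29 − 15 = 14 days.

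These gaps belong to the visit schedule, not to the unscheduled-results rule. They show only that a transient change can arise and resolve without meeting a planned draw.

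**Step 2: follow an illustrative value (all results assumed).** Take a parameter with an upper limit of 40 and a Part B participant with baseline 30. Scheduled results are 35 (Day 8), 38 (Day 15), 39 (Day 28) and 30 (Day 56). An unscheduled Day 20 result is 150.

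| Output | What it shows |
|---|---|
| By-visit summary | Participant's largest post-baseline value 39 |
| Shift from baseline | Normal to Normal at every visit |
| Out-of-range counts | 0 at every scheduled time point |
| Full and abnormal laboratory listings | 150, flagged High |

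The visible shift shells (Tables 14.3.4.1.2, 14.3.4.2.2 and 14.3.4.4.2) have no worst-value or any-time row that would pick up the 150.

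**Step 3: could it enter by another door?**

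- *TEAE tables.* If the change is an SAE or leads to discontinuation, Protocol 8.3 requires an AE and it is counted. If the participant has symptoms, those are AEs and are counted. A non-serious change in a laboratory value, blood pressure or pulse that does not stop treatment need not be recorded, so it may reach no TEAE table.
- *Early termination.* SAP 3.5 summarises these assessments with end of study, so they are not excluded. They are a separate category from unscheduled visits.
- *Follow-up.* SAP 3.1 defines follow-up as the latest usable value after the final dose, which might admit a late unscheduled result. The shells fix it at Day 29 (Part A) or Day 56 (Part B). This does not help with a Day 20 value.
- *Listings.* Listings 16.2.8.1.2 and 16.2.8.2.2 show abnormal laboratory results at all visits. The listing index has no equivalent for vital signs; Listing 16.2.9.1 shows all values with a High/Low flag.

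**Step 4: weight of one omitted participant.** With n participants in a group, one adds 100/n percentage points. Group sizes come from SAP 2.1.

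| Group | n | 0/n to 1/n |
|---|---|---|
| Part A | 2 | 50.0 points |
| Part B, one LMN-101 dose | 4 | 25.0 points |
| Part B, pooled placebo | 6 | 16.7 points |
| Part B, LMN-101 overall | 12 | 8.3 points |

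The documents do not say how often unscheduled tests occur or why. If no participant has an abnormality of this kind, the effect is zero.

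**The case against.** The strongest reply is that nothing is lost. Every unscheduled value is listed, the abnormal laboratory listings carry flags, clinical significance and changes from baseline and follow-up, and the trial has 20 participants. A careful reader can find any abnormal laboratory result quickly. This stands as real mitigation, but a listing does not correct a table that reports zero, and vital signs have no listing of abnormal values alone.

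Four stronger readings are tempting, and the documents do not support them:

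- *That such findings are barred from every safety table.* TEAE tables count events, not visits. Symptoms, SAEs and changes leading to discontinuation found at an extra visit are tabulated there. An investigator may also record other changes as AEs, since Protocol 8.3 waives the duty without forbidding it. The waiver does not name temperature or respiratory rate.
- *That the rule generally biases the tables toward no change.* If a scheduled result is abnormal and a normal retest follows, excluding the retest keeps the abnormal value in the tables. The rule then preserves the signal.
- *That allowing unscheduled values for baseline but not afterwards is itself an error.* Baseline is one value per participant, the latest before dosing. Day 1 laboratory tests are required only when screening tests are more than 2 weeks old, so accepting a pre-dose repeat is sensible. Restricting by-visit summaries to scheduled visits is also sound.
- *That 25 points is the size of a bias.* It is 1/4, conditional on one hypothetical participant.

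**Conclusion.** The point holds in a limited form. Followed exactly, the plan can tabulate no abnormality for a component of the primary safety endpoint when one was observed. This applies to laboratory, blood pressure or pulse changes that are seen only at an unscheduled post-dose visit, are not serious, do not end treatment and are not voluntarily recorded as AEs. Such a change would be found only in listings.

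The weight of one such participant is 25.0 percentage points at a Part B dose level (0/4 to 1/4) and 8.3 points in Part B LMN-101 overall (0/12 to 1/12). No expected size can be given without the frequency of unscheduled tests. Because the values remain listed, this is a reporting gap that should be closed, not a threat to the validity of the data. It does not depend on any assumption about why unscheduled tests are drawn.

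**What to change.** Keep the by-visit summaries on scheduled visits and leave the baseline rule as it is. Then:

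1. Reword SAP 3.1, 12.3.1, 12.4.1 and the mock-table general comments so that the scheduled-only rule applies to by-visit summaries alone.
2. Add two rows, lowest and highest post-baseline value from all scheduled and unscheduled results, to shift Tables 14.3.4.1.2 and 14.3.4.2.2 and to the out-of-range counts. Two rows are needed because a parameter can be abnormal in either direction.
3. In Part B, split these rows into on-treatment and follow-up. In Part A, which has a single dose, use one post-dose period.
4. Add the same rows to Table 14.3.4.4.2. Its Low/Normal/High classification already needs normal ranges, which SAP 12.4.1 does not give, so the SAP must state them.
5. Footnote the number of assessments behind each worst-value row, because participants tested more often have more chances of an abnormal result.

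The cost is SAP and shell wording plus derived rows: 2 × 2 = 4 per parameter for each Part B group and 2 for Part A. No new data are needed. The remaining drawback is unequal testing between participants, which the footnote discloses but does not remove.
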